Appendix B

Appendix B

-		UNMATCHED	
		Optum	
Variable Number of patients	Glimpiride 3,096	Liraglutide 378	St. Diff
Age squared			
mean (sd) ge (continuous)	761406 (223830.2)	651214 (225218.8)	0.491
mean (sd) te (categories)	64.24 (10.37)	59.22 (10.94)	0.471
8 - 40; n (%)	95 (3.1%)	20 (5.3%)	-0.110
1 -50; n (%) 1 -60; n (%)	266 (8.6%) 602 (19.4%)	64 (16.9%) 106 (28.0%)	-0.251 -0.203
- 70; n (%) - 80; n (%)	1187 (38.3%)	133 (35.2%) 55 (14.6%)	0.064 0.390
ler	946 (30.6%)		
: MALE; n (%) FEMALE; n (%)	1726 (55.7%) 1370 (44.3%)	179 (47.4%) 199 (52.6%)	0.167 -0.167
ite; n (%) white; n (%)	1492 (48.2%) 1604 (51.8%)	220 (58.2%) 158 (41.8%)	-0.201 0.201
ndar time years (Jan 2010 - Jun 2020)			
n 26, 2010 - Dec 31, 2017; n (%) n 1, 2018 - Jun 30, 2020; n (%)	1850 (59.8%) 1246 (40.2%)	255 (67.5%) 123 (32.5%)	-0.161 0.161
al Health			
ng; n (%) y or Overweight; n (%)	296 (9.6%) 760 (24.5%)	30 (7.9%) 93 (24.6%)	0.060 -0.002
ty; n (%) reight: n (%)	554 (17.9%) 247 (8.0%)	79 (20.9%) 16 (4.2%)	-0.076 0.159
ned comorbidity score, 180 days			
(sd) core: Empirical Version 180 days	2.06 (1.56)	1.86 (1.36)	0.137
(sd)	0.99 (0.77)	1.03 (0.73)	-0.053
bA1c	8.16 (0.96)	8.18 (0.99)	-0.021
sd) scular Comorbidities			
sion; n (%) demia; n (%)	391 (12.6%) 2296 (74.2%)	66 (17.5%) 299 (79.1%)	-0.137 -0.116
erosis Disease (MI, angina, CAD and other forms of chronic ischemic	566 (18.3%)	43 (11.4%)	0.116
ease, History of CABG or PTCA); n (%) : n (%)	64 (2.1%)	3 (0.8%)	0.195
vII; n (%)	10 (0.3%)	1 (0.3%)	0.000
nstable angina; n (%) angina; n (%)	18 (0.6%) 80 (2.6%)	1 (0.3%) 6 (1.6%)	0.045 0.070
other forms of chronic ischemic heart disease; n (%)	415 (13.4%)	30 (7.9%)	0.179
y of CABG or PTCA; n (%)	107 (3.5%)	9 (2.4%)	0.065
r PAD surgery; n (%) vascular disease (Stroke, TIA, Late effects); n (%)	166 (5.4%) 77 (2.5%)	11 (2.9%) 2 (0.5%)	0.126 0.165
e (Ischemic or hemorrhagic); n (%)	40 (1.3%)	1 (0.3%)	0.112
n (%) effects of cerebrovascular disease; n (%)	27 (0.9%) 28 (0.9%)	1 (0.3%) 0 (0.0%)	0.078 0.135
ailure; n (%) brillation: n (%)	103 (3.3%)	10 (2.6%)	0.041
illation; n (%) diac dysrhythmia; n (%)	121 (3.9%) 190 (6.1%)	14 (3.7%) 18 (4.8%)	0.010 0.057
s Mellitus Comorbidities			
remia; n (%) nephropathy; n (%)	20 (0.6%) 434 (14.0%)	4 (1.1%) 48 (12.7%)	-0.054 0.038
Neuropathy; n (%)	495 (16.0%)	60 (15.9%)	0.003
: Retinopathy; n (%) is with unspecified complications; n (%)	134 (4.3%) 122 (3.9%)	20 (5.3%) 14 (3.7%)	-0.047 0.010
es with peripheral circulatory disorders and amputations, DF; n (%)*	70 (2.3%)	9 (2.4%)	-0.007
etes with peripheral circulatory disorders; n (%) er-limb amputations; n (%)	38 (1.2%) 4 (0.1%)	5 (1.3%) 1 (0.3%)	-0.009 -0.045
tic Foot; n (%)	32 (1.0%)	3 (0.8%)	0.021
omorbidities : kidney disease stages I-IV and NOS; n (%)	381 (12.3%)	40 (10.6%)	0.053
laneous renal disease; n (%)	109 (3.5%)	10 (2.6%)	0.052
disorders (Anxiety and Depression); n (%) ety; n (%)	332 (10.7%) 211 (6.8%)	47 (12.4%) 27 (7.1%)	-0.053 -0.012
sion; n (%)	162 (5.2%)	28 (7.4%)	-0.091
morbidities ive sleep apnea; n (%)	259 (8.4%)	41 (10.8%)	-0.082
%)	207 (6.7%)	9 (2.4%)	0.207
n (%) hrosis: n (%)	96 (3.1%) 363 (11.7%)	14 (3.7%) 49 (13.0%)	-0.033 -0.040
FLD; n (%)	98 (3.2%)	16 (4.2%)	-0.053
ons	2585 (83.5%)	324 (85.7%)	-0.061
rtensive medications; n (%) RBs; n (%)	2257 (72.9%)	285 (75.4%)	-0.061
ckers; n (%) channel blockers; n (%)	971 (31.4%) 795 (25.7%)	94 (24.9%) 83 (22.0%)	0.145 0.087
channel blockers; n (%) : n (%)	369 (11.9%)	52 (13.8%)	-0.057
cs; n (%)	1108 (35.8%)	133 (35.2%)	0.013
ther lipid-lowering drugs; n (%) : n (%)	2402 (77.6%) 2285 (73.8%)	291 (77.0%) 273 (72.2%)	0.014 0.036
(%)	370 (12.0%)	49 (13.0%)	-0.030
zing Medications; n (%)	507 (16.4%) 719 (23.2%)	72 (19.0%) 129 (34.1%)	-0.068 -0.243
ts; n (%)	540 (17.4%)	105 (27.8%)	-0.251
/hypnotics; n (%) pine; n (%)	114 (3.7%) 256 (8.3%)	25 (6.6%) 42 (11.1%)	-0.131 -0.095
ids; n (%)	319 (10.3%)	49 (13.0%)	-0.084
lization dication claims			
1)	11.47 (6.60)	12.82 (6.94)	-0.199
of office visits sd)	4.76 (3.58)	5.24 (3.72)	-0.131
hospitalizations or ED visits			
) Endocrinologist visits	0.24 (0.87)	0.20 (0.66)	0.052
sd)	0.13 (0.55)	0.27 (0.85)	-0.196
of HbA1c test orders sd)	1.77 (0.68)	1.79 (0.78)	-0.012
l) lexible Sigmoidoscopy or colonoscopy or CT virtual colonoscopy (CRC	1.77 (0.68)	1.79 (0.78)	-0.012
ng); n (%)		,,	
	400 (12.9%) 120 (3.9%)	59 (15.6%) 16 (4.2%)	-0.077 -0.015
	659 (21.3%)	93 (24.6%)	-0.079
r of Pap smear (Cervical cancer screening); n (%) cine; n (%)	671 (21.7%)	82 (21.7%)	0.000
of Pap smear (Cervical cancer screening); n (%) ine; n (%) scoccal vaccine; n (%)		0.03 (0.18)	0.002
r of Paps smear (Cervical cancer screening); n (%) icine; n (%) scoccal vaccine; n (%) or DDAR tests (sd)	0.04 (0.19)	0.03 (0.18)	
of Paps mear (Cervical cancer screening); n (%) ine; n (%) occacial vaccine; n (%) of DXA tests (sd) or pharmacy cost (charges in U.S. \$)			-D 331

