5.2.1 Eligible cohort entry dates

Liraglutide indication as an adjunct to diet and exercise to improve glycemic control in adults with type 2 diabetes mellitus was approved by FDA on Jan 25, 2010 (the approval of glimepiride for the same indication was antecedent to 2010). Thus, the initial eligible cohort entry date is the first date after the FDA approval available in the data. The last eligible date is June 30, 2020, three months before the end of all available data in Optum CDM. Since the effects of liraglutide and glimepiride on the outcome (i.e., change in HbA1c) will be estimated between 56 and 212 days after cohort entry (see Section 6.3), this will allow all eligible patients to contribute to the outcome. The database used is Optum CDM because lab results/values are available in this database for a subset of laboratory tests, including the A1C tests. The following eligible cohort entry dates were included:

- Optum CDM: Jan 26, 2010 Jun 30, 2020
- 5.2.2 Specify inclusion/exclusion criteria for cohort entry and define the index date Inclusion and exclusion criteria were adapted from the trial as closely as possible. Definitions for all inclusion/exclusion are provided in **Appendix A** and are summarized in the flowcharts below.

Note. Patients who are censored between cohort entry and the beginning of the outcome assessment window (i.e., 0.x-56 days after cohort entry) for the reasons reported in the Section 6.3.2 will not contribute to the unmatched or matched cohorts. Further details on the number of patients who are excluded from the study cohort are reported in the Section 7.

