• Stop analyses until feasibility and power are reviewed by primary investigators and FDA. Reviewers evaluate the results of the analyses described above in Sections 7 and 8, including numbers of patients, patient characteristics, follow-up time, and reasons for censoring by treatment group, as well as overall rates of outcomes and study power. These parameters are re-evaluated and reported in the subsequent sections, after incorporating feedback and refining the protocol.

o Optum CDM

Non-inferiority Analysis	
Standard deviation of outcome	1.01
Non-inferiority limit	0.4
Alpha (2-sided)	0.05
Power (1-beta)	90%
Sample size required per group	110
Total sample size required	220
Number of patients matched	752
Reference	376
Exposed	376

• Stop analyses until feasibility and power are reviewed by primary investigators, FDA, and assigned members of advisory board.

Reviewed by PI:	[name]	Date reviewed:	07/16/2021
Reviewed by FDA:	[name]	Date reviewed:	08/2/2021
Reasons for stopping			
analysis (if required):			

9. Balance Assessment

For liraglutide vs. glimepiride

Optum CDM: see file LEAD-2_programming_steps and output of "STEP 3 - BALANCE Assessment (with dummy outcome) - Paragraphs 9-10 of the protocol"

Date conducted: 06/16/2021

After review of initial feasibility and power analyses, complete creation of the remaining covariates from Section 6.2. Again, using the dummy outcome of a 90-day gap in database enrollment, complete a 1:1 PS-matched analysis. The PS should include the complete list of covariates.

• Provide plot of PS distributions stratified by treatment group.

Note- Please refer to Appendix B.

• Report covariate balance after matching.

Note- For Table 1, please refer to **Appendix B**.

• Report reasons for censoring by treatment group.

	Overall (n. 746)	Liraglutide – exposure (n. 373)	Glimepiride – comparator (n. 373)
Outcome (dummy)	0 (0%)	0 (0%)	0 (0%)
Death	0 (0%)	0 (0%)	0 (0%)
Start of an additional exposure	9 (1.2%)	6 (0.8%)	3 (0.4%)
End of index exposure	194 (26.0%)	137 (18.4%)	57 (7.6%)
Maximum follow-up time	340 (45.6%)	137 (18.4%)	203 (27.2 %)
End of patient data	5 (0.7%)	3 (0.4%)	2 (0.3%)
End of patient enrollment	61 (6.3%)	25 (3.4%)	36 (4.8%)
Start of additional antidiabetic drugs + Nursing home + Metformin discontinuation with allowed 60 days gap	137 (18.4%)	65 (8.7%)	72 (9.7%)

• Report follow-up time by treatment group.

Median Follow-Up Time (Days) [IQR]			

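### Calendar time over a 10.4-year entry window is listed for the propensity score as two blocks, one 7.9 years long, so secular confounding within a block is not controlled and could remain

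*Combined protocol and SAP*

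**What the plan says.** Section 5.2.1 sets the entry window as "Optum CDM: Jan 26, 2010 Jun 30, 2020" and confirms that "The last eligible date is June 30, 2020".

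Appendix B Table 1 has one calendar-time covariate. Its heading reads in part "time years (Jan 2010 - Jun 2020", and its row labels, with their first letters clipped, read "n 26, 2010 - Dec 31, 2017; n (%) n 1, 2018 - Jun 30, 2020; n". The unmatched counts are "1850 (59.8%) 1246 (40.2" for glimepiride and "255 (67.5%) 123 (32.5" for liraglutide, with a standardised difference of 0.161 in absolute value.

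Section 6.2 refers to this table for the covariates beyond age, gender and comorbidity index. For the 1:1 match, Section 9 states: "The PS should include the complete list of covariates". The readable text contains no entry year, continuous entry date, exact matching on time or calendar-time sensitivity analysis. Age, by contrast, is listed in three forms: continuous, squared and in five categories.

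**The concern.** In a cohort that accrues over a decade, the choice between an injectable drug and an older oral drug can drift, and so can background care and the recording of diagnoses. If the HbA1c change after starting treatment drifts too, entry date is a confounder. A two-level term removes only the difference between the blocks. Within the first block, a 2010 entry and a 2017 entry carry the same value, so the score has no direct information on timing there. A balance table built on the same two levels would look satisfactory whatever the timing within them.

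The documents themselves supply one link between entry date and outcome measurement. By Section 5.2.1 the data end about three months after the last entry date, while the HbA1c window runs to day 212. Patients entering after about 2 March 2020 therefore have a shortened window, down to about 92 days for the last entrants, and the late block pools them with 2018 entrants. This link is small: Section 7 shows 37 patients censored at end of data.

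At stake is a possible bias in a difference to be judged against a 0.4 margin.

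**Working it through.** **Inputs.** Entry dates from Section 5.2.1; block dates, counts and standardised difference from Appendix B Table 1; 373 matched pairs and outcome SD 1.01 from Sections 9 and 10; margin 0.4 from Section 1.4.

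**1. Completeness of the two categories.** Glimepiride: 1850 + 1246 = 3,096. Liraglutide: 255 + 123 = 378. Both equal the full arms, so there is no third category.

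**2. The plan's own figure.** Standardised difference = (p1 − p2) / √{[p1(1 − p1) + p2(1 − p2)] / 2}, with p1 = 1850/3096 = 0.5975 and p2 = 255/378 = 0.6746. This is −0.0771 / √[(0.2405 + 0.2195)/2] = −0.0771/0.4796 = −0.161. It reproduces. It is a between-block, pre-matching figure.

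**3. Block lengths.** The full window is 10.43 years, the early block 7.93 years (76% of it) and the late block 2.50 years.

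**4. Treatment choice by block.** Liraglutide is 255/2105 = 12.1% of initiators early and 123/1369 = 9.0% late; odds ratio (255/1850)/(123/1246) = 1.40.

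**5. How much timing the two levels miss (assumption: uniform entry within each block).** Within-block variance is the weighted sum of length²/12; between-block variance is p(1 − p) times the squared distance between block midpoints, (7.93 + 2.50)/2 = 5.21 years.
- Glimepiride: within 3.34, between 6.54, so 34% of the variance in entry date lies inside blocks.
- Liraglutide: within 3.71, between 5.97, so 38%.

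The mean gap between two random entrants in one block is length/3: 2.64 years early and 0.83 late. Weighted to liraglutide this is 0.675 × 2.64 + 0.325 × 0.83 = 2.05 years. With one-year categories it would be 1/3 = 0.33 years.

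**6. Possible bias (gap and drift are assumptions).** Bias = early-block share of liraglutide × gap in mean entry between arms inside that block × yearly drift in the 26-week HbA1c change.
- Gap 1 year, drift 0.03: 0.675 × 1 × 0.03 = 0.020, or 5% of 0.4.
- Gap 1 year, drift 0.05: 0.675 × 1 × 0.05 = 0.034, or 8% of 0.4.
- Wider range, gap 0.5 to 3 years and drift 0.01 to 0.10: 0.003 to 0.20.

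For scale, the 95% interval half-width is about 1.96 × 1.01 × √(2/373) = 0.145. This uses the SD of follow-up HbA1c as in Section 10 and treats every matched patient as having an outcome.

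**The case against.** The strongest reply is that the harm is hypothetical. Confounding within a block needs arms that differ in timing inside the block and an HbA1c change that varies with calendar time, and the documents give neither. That stands. It rules out several stronger readings.

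- A reader might infer that secular confounding is present in the matched comparison. The documents support only that it is not controlled within blocks.
- A reader might take the 0.161 as evidence of imbalance inside the long block. It compares the blocks before matching, and it is the difference the score is meant to remove. The matched columns of Table 1 are not readable in the text available, so nothing is claimed about them.
- A reader might say that pairs are matched on time block. Matching is on the score, no exact match on block is stated, and a pair may cross blocks.
- A reader might apply the assumed drift to the whole cohort and reach 8% to 13% of the margin. The gap is assumed only inside the early block, so the 67.5% weight applies.
- A reader might place the change from ICD-9 to ICD-10 inside the early block. The documents give no changeover date, and Appendix A describes a forward/backward code mapping.

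Some routes are also partly closed. The outcome is a change from a baseline taken within 90 days before entry. Baseline HbA1c is a listed covariate (8.16 versus 8.18 unmatched), so drift in HbA1c level is largely removed and mainly drift in the change matters. All patients need three HbA1c results in the prior year, and the count of test orders is listed and nearly equal (1.77 versus 1.79).

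Finally, the footnote marking variables in the score relies on asterisks that are mostly not legible. Two-level entry of calendar time is thus a fair inference from Section 9 and Table 1, not an explicit statement. If a finer term was in fact used, the plan should say so.

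**Conclusion.** The point holds as a limited improvement. As listed, calendar time is too coarse for a 10.4-year window: entries up to 7.9 years apart are indistinguishable to the score on time, and imbalance within a block cannot be seen in the balance table. Treatment choice varies between the blocks before matching, which makes finer control reasonable but does not establish confounding inside them.

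Under the central assumptions the bias is about 0.02 to 0.034 HbA1c points, small beside both the margin and the likely interval half-width. It becomes material only if the timing gap and the drift are both large; the assumed extreme of 0.20 is half the margin. The direction is unknown, since the documents report neither quantity.

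**What to change.** Replace the two-level variable in the propensity score with calendar year of cohort entry (indicators) or a spline of entry date. Rerun the match, and report matched balance on entry year or date in Table 1.

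The data look able to support it. Average entries per year are about 255/7.93 = 32 liraglutide and 1850/7.93 = 233 glimepiride in the early block, and 123/2.50 = 49 and 1246/2.50 = 499 in the late block.

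The cost is one covariate redefinition, a rerun of the match and possibly a few of the 373 pairs, against a stated requirement of 110 per group. The comparative-analysis section (Section 13) is still blank, so the change can be made before any treatment effect is reported.
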